SS-OCTA: Images will be obtained using the Zeiss PLEX Elite 9000, which is a quick, inexpensive, and non-invasive method for acquiring retinal images with an axial resolution of ~5µm and a scan depth of 3.0mm. Automated layer segmentation provides four horizontal depth-resolved retinal slabs: superficial (SRL), deep (DRL), outer retinal layer (ORL) and the choriocapillaris. Participant images will be excluded for low signal strength (≤6), blink artifacts, doubling artifacts, media opacity obscuring visualization of the vasculature, and/or segmentation errors. Manual segmentation editing will be conducted to ensure proper layer assessment. Microvessels for the SRL, DRL, and choriocapillaris slab will be processed using a custom semiautomated algorithm we developed to rapidly quantify several vessel parameters including vessel density, length, diameter, and capillary network. All images will be independently analyzed and compared among study subjects by two graders blinded to the group assignment.

Outcome: Primary outcomes include the change in PANSS positive and negative scores (2hrs, 5hrs, 1wk, 2wk, and 4wks) in the SNP group compared to placebo. The secondary outcomes include the change in overall cognition (0hr, 1wk, 2wk, and 4wks) and retinal microvascular measures (0hr, 5hrs), as well as examining the relationship between baseline or change in retinal vessel measures or CRP and the change in psychosis symptoms and cognition after SNP treatment compared to placebo.

SNP Treatment Protocol

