- All side effects and vital parameters will be recorded during the infusion and 2 hours following the infusion by CRC nursing.
- Any abnormal, clinically significant vital signs will be recorded as adverse events.

Discharge Procedure

- Gross motor and cognitive function, ataxia, reflexes/clonus will be evaluated and documented by a study PI ([name]) prior to discharge.
- Before being discharged patients should be awake and alert, feeling well, with no nausea, vertigo, or dizziness.
- There should be no significant change in vital signs from prior to infusion.
- They will be given a small meal before discharge from the CRC.
- Patients will be instructed not to drive. If necessary, the study nurse will release them to the
 care of an adult family member or caregiver, who will accompany the patient home. If
 needed, a trained Research Assistant will contact the participants support system to ensure
 transportation is coordinated.

Study Drug Handling

- Nitroprusside will be compounded by research pharmacy in 5% dextrose
- 5% dextrose will be used as placebo
- Study drug will be stored at room temperature and the required amount will be released from the pharmacy to the CRC at the time a patient is scheduled for the protocol.
- Study drug will be provided in light-blocked bags with labeling to ensure blinding of study staff.

Nitroprusside standard concentration is 50mg/250mL of D5W and the concentrated version is 100mg/250mL.

Institutional Approvals

Critical Care Executive – [name] and [name] – Approval granted on 9/8/21 Critical Care Practice – [name] and [name] – Approval granted on 9/8/21

B. Statistical Considerations

Power calculation: With 16 ECS individuals in the SNP group and 16 in the placebo group we will have >80% power to detect a 10-point PANSS difference between the placebo and treatment groups, with a SD of 6, alpha of 0.05, 2-sided alternative hypothesis, 2-sample t-test, based on the sample size suggested by the retinal vessel differences in our pilot data. The above-mentioned sample size was determined based on our pilot SS-OCTA data, which suggests that we will have >70% power to detect group differences of at least 0.007 (estimated standard deviations of skeletal density =0.008, significance level=0.05, two-sided t-tests).

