Baseline demographic details will be compared between the SNP and placebo groups using independent-samples t tests or Mann-Whitney U tests where appropriate using R software. Categorical data will be compared using chi-square tests. Effect sizes will be provided using Cohen's d. The primary outcome (PANSS) will be analyzed using a 2 (treatment group) × 5 (time point) mixed analysis of variance (ANOVA). Analyses of secondary outcome measures will be compared using a 2-group x 4 time point mixed ANOVA for cognition and a 2 x 2 for retinal measures. The relationship between baseline or change in retinal vessel measures or CRP and change in PANSS scores or cognition will be performed using Pearson's (parametric) or Spearman's (non-parametric) correlation.

C. Subject Selection

Population: Men and women, 18-60 years of age, from diverse background, symptomatic, with early course schizophrenia, and meet all study inclusion and exclusion criteria.

Inclusion criteria for ECS patients are: a DSM-V diagnosis of SZ or schizoaffective disorder with ≤5 years from the onset of psychosis and up to 2 years of lifetime exposure to antipsychotics, total score of ≥55 on the PANSS with a score of ≥3 on 1 or more PANSS Positive Scale items (delusions, conceptual disorganization, hallucinatory behavior, suspiciousness, or unusual thought content) and/or score of ≥3 on the CGI-S scale, taking antipsychotic for 8 weeks with a stable dose of 4 weeks (no medication change will be allowed during the trial), English proficiency, understands and is able, competent and willing to give informed consent in accordance with the International Conference on Harmonization Good Clinical Practice Guidelines.

Exclusion criteria are:

- Presence of renal, hepatic, cardiac, hematologic, neurologic impairments or abnormal physical exam.
- Presence of retinal disease (myopia >4.0 diopters)

- Baseline systolic BP <100mmHg or symptomatic orthostatic hypotension (systolic BP <90 mmHg or diastolic BP <60 mmHg) with any of the following: lightheaded or dizzy, blurry vision, weakness, syncope, confusion, nausea.
- Pregnant or breastfeeding (pregnancy test at screening visit and prior to randomization).
- Abnormal laboratory testing (see appendix)
- Treatment with medications that may interfere with the metabolism or excretion of SNP or are associated with drug-drug interactions (see list of medications below).
- Prior history of intolerance to SNP
- Currently taking clozapine or chlorpromazine

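### The cognition and retinal ANOVAs enter the 0hr value as an outcome level, do not adjust for it, and do not say which term tests SNP

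*Combined protocol and SAP*

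**What the plan says.** B3.A (Outcome) gives the secondary outcomes as "change in overall cognition (0hr, 1wk, 2wk, and 4wks) and retinal microvascular measures (0hr, 5hrs"), each compared with placebo. That is four times for cognition and two for the retina, with 0hr among them in both cases. B3.B then says these outcomes will be "compared using a 2-group x 4 time point mixed ANOVA for cognition and a 2 x 2 for retinal measures". Four and two levels match the lists only when 0hr is counted. The section mentions no covariate and does not say whether the group main effect or the group x time interaction is the test of SNP.

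The primary outcome is laid out differently. It is the "change in PANSS positive and negative scores (2hrs, 5hrs, 1wk, 2wk, and 4wks"), "analyzed using a 2 (treatment group) × 5 (time point) mixed analysis of variance (ANOVA"), so its five levels match five post-dose times and 0hr is not among them. The point here concerns the secondary outcomes only.

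The sample size is "With 16 ECS individuals in the SNP group and 16 in the placebo group". The retinal justification is ">70% power to detect group differences of at least 0.007" ("estimated standard deviations of skeletal density =0.008, significance level=0.05, two-sided t-tests").

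**The concern.** The 0hr value precedes the infusion, so under randomisation the expected difference between arms at that time is zero. A mixed ANOVA with 0hr as a level offers two terms that could be reported as the SNP result, and they answer different questions. The group main effect averages a known null into the post-dose difference. The interaction recovers the change versus placebo, but it subtracts the baseline in full instead of weighting it by its correlation with the outcome. For cognition it also spreads the test over three degrees of freedom.

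Purpose 2 in B1 includes the effect of SNP on cognition and retinal phenotypes. With 32 patients there is little precision to spare. With the term unnamed, two analysts could follow the same text and report very different sensitivity.

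**Working it through.** **Inputs.** From B3.B: n = 16 per arm, two-sided alpha 0.05, retinal difference 0.007, SD 0.008, so d = 0.007/0.008 = 0.875. Assumed, because the documents give no figure: equal SDs, one common correlation ρ between times, and the cognition effect sizes.

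**The plan's own figure.** Two-sample comparison, noncentrality 0.875 × √(16/2) = 2.475. Power is 69.7% by the normal approximation and 66.8% by the exact t-test. The stated figure of more than 70% is therefore close but slightly high; the exact test passes 70% at 18 per arm.

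**Retina, 2 x 2.** Let b = (n/2)d² = 8 × 0.7656 = 6.125. Noncentralities:

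- Group main effect (estimates d/2): b/[2(1+ρ)]
- Group x time, the same as a change-score t-test (estimates d): b/[2(1−ρ)]
- ANCOVA on 0hr (estimates d): b/(1−ρ²)

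At ρ = 0.5 these are 6.125/3 = 2.04, 6.125/1 = 6.13 and 6.125/0.75 = 8.17. Power from the noncentral F (1 and 30 df; 29 for ANCOVA):

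| ρ | Main effect | Group x time | ANCOVA |
|---|---|---|---|
| 0.3 | 32% | 53% | 71% |
| 0.5 | 28% | 67% | 79% |
| 0.6 | 27% | 76% | 85% |
| 0.7 | 26% | 87% | 92% |
| 0.8 | 24% | 97% | 98% |
| 0.9 | 23% | about 100% | about 100% |

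The efficiency of the change score relative to ANCOVA is (1+ρ)/2: 0.75 at ρ = 0.5 and 0.90 at ρ = 0.8. Below ρ = 0.5 the change score has less power than a t-test of the 5 h value alone (66.8%).

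**Cognition, 2 x 4, constant effect d at weeks 1, 2 and 4.** With b = 8d²:

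- Group main effect (estimates 3d/4): (9/16)b/[(1+3ρ)/4]
- Group x time: 0.75b/(1−ρ) on 3 and 90 df
- Post-dose mean minus 0hr, with 0hr kept as a level: the same noncentrality on 1 and 30 df
- Post-dose mean adjusted for 0hr: b/[(1+2ρ)/3 − ρ²] on 1 and 29 df

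At d = 0.6 and ρ = 0.6, b = 2.88:

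- Main effect: 2.88 × 0.5625/0.7 = 2.31, power 31%
- Interaction: 0.75 × 2.88/0.4 = 5.40, power 45%
- One-df contrast: 5.40, power 61%
- Adjusted mean: 2.88/0.3733 = 7.71, power 77%

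Of the 32 points between 45% and 77%, 16 come from focusing the contrast and 16 from adjusting for baseline.

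**Cognition, fading effect of 0.6, 0.3 and 0 at weeks 1, 2 and 4, ρ = 0.6.** The arm differences including 0hr are 0, 0.6, 0.3, 0. Their mean is 0.225 and their sum of squared deviations is 0.45 − 4 × 0.225² = 0.2475.

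- Interaction: 8 × 0.2475/0.4 = 4.95, power 42%
- Adjusted average: 8 × 0.3²/0.3733 = 1.93, power 27%
- Unadjusted post-minus-0hr average: 0.72/0.5333 = 1.35, power 20%

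For an effect of 0.6 at week 1 only, the interaction has 45% and the adjusted average 15%. The averaged contrast is what loses here; for that same contrast, the covariate still helps (27% against 20%).

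**Simulation check.** 20,000 trials per setting, at ρ = 0.5 and 0.8, agreed with the formulas. The simulated ANCOVA figures were up to about 1.5 points lower (for example 78.0% against 78.9% for the retina at ρ = 0.5).

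**The case against.** A mixed ANOVA with baseline as a level is a valid analysis. B3.A defines both outcomes as change versus placebo, and in a pre/post layout that is the group x time term. Under randomisation this term is unbiased, and including 0hr does not inflate its type I error. A reader might infer from the layout that the planned analysis dilutes the SNP effect. The documents do not support that: dilution belongs to the group main effect alone, and the plan does not name that effect as the test.

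A reader might also infer that the planned models are clearly less sensitive for both outcomes. That does not hold in general either. The retinal scans are taken about 5 hours apart, so a high correlation is plausible (an assumption), and at 0.8 or above ANCOVA gains about 1 point or less. For cognition, about half the apparent gain at d = 0.6 and ρ = 0.6 is the choice of a focused contrast. If the effect of a single infusion fades, the omnibus interaction can beat the average over visits.

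These objections stand. They leave untouched that the tested term is unnamed, that one available reading performs poorly, and that a baseline value already collected goes unused as a covariate.

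**Conclusion.** The point holds as a gap in specification with an efficiency cost. It is not an error that invalidates the secondary analyses. Two parts are firm. First, B3.B does not name the test, and reading the main effect as the test gives half or three quarters of a constant effect. Second, ANCOVA on 0hr was at least as powerful as either 2 x 2 term for the retina over the whole range of ρ examined.

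If group x time is meant, the retinal loss is 18 points at ρ = 0.3, 12 at 0.5, 5 at 0.7 and about 1 at 0.8. The documents do not show where ρ lies. The cognition figures rest on an assumed effect size, and their direction on the assumed shape over time. They support adding the covariate; they do not settle which contrast is best. As these are secondary outcomes of a pilot trial, this is an improvement worth making before unblinding.

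**What to change.** In B3.B, replace the two secondary ANOVAs as follows.

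- **Retina:** ANCOVA of the 5 h value on arm and the 0hr value.
- **Cognition:** a repeated-measures model of the week 1, 2 and 4 scores with arm, visit, arm x visit and the 0hr score as covariate.
- **Reporting:** adjusted differences with 95% CIs, per visit for cognition.
- **Cognition contrast:** name it in advance. The average over the three visits gains power if the effect is sustained and loses power if it fades. The choice is the sponsor's and should follow from the time course it expects.

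If the ANOVAs are kept, state that group x time, not the group main effect, is the test of SNP.

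The cost is SAP wording and about one degree of freedom per model. The 0hr values are already scheduled, so no visit, assessment or patient is added.

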NCT Number: NCT04986072

Official Title: Sodium Nitroprusside in Early Course Schizophrenia

Document Type: Study Protocol and SAP

Document Date: 07/17/2023

PART B STUDY DESCRIPTION

Title of Protocol	Proof of Mechanism Study using a Retinal Biomarker to Predict Treatment Response with Intravenous Sodium Nitroprusside in Symptomatic Early Course Schizophrenia
Principal Investigator	[name]

B1. PURPOSE OF PROTOCOL

- 1. The main purpose of this proposal is to determine the effectiveness of a single intravenous administration of sodium nitroprusside (SNP) (0.5 mcg/kg/min for 4 hours) on positive and negative symptoms in symptomatic Early Course Schizophrenia (ECS).
- 2. To examine the effect of SNP on cognition and retinal imaging phenotypes in ECS, and whether baseline retinal microvasculature or inflammation (CRP levels) correlate with a change in psychosis symptoms or cognition.

We hypothesize that SNP will improve psychosis symptoms and cognition in symptomatic ECS and that this change can be predicted by retinal vessel morphology or CRP levels. We predict that SNP will improve oxygen supply and reduce inflammation, which will be evidenced by reductions in retinal vessel phenotypes.

B2. SIGNIFICANCE AND BACKGROUND FOR THE STUDY

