Nitric oxide (NO) signaling is a potential mechanism for protecting the microvasculature against oxidative stress, inflammation and endothelial dysfunction¹⁶. NO-donors (NOD) can protect nerve tissue from injury and preserve the integrity of the blood brain barrier, suggesting that cerebral vascular endothelium is essential in the control of vascular inflammatory and oxidative responses, leukocyte migration, and the production of inflammatory mediators¹. In addition to reducing oxidative stress and inflammation, NOD can increase cerebral and retinal blood flow¹⁶. In healthy volunteers, SNP dose dependently increases retinal arteriolar/venular diameter, and leukocyte flow¹⁷. However, in pathologic states such as ischemia, SNP can enhance neuroprotection by increasing arteriolar diameter and reducing venular leukocyte adhesion (i.e., reduced venular diameter), which together facilitate blood flow¹⁶. Preclinical and clinical evidence have shown that SNP may have an antipsychotic profile. In preclinical studies, SNP has been used to prevent SZrelated behaviors in a spontaneously hypertensive rat model¹⁸. Five clinical studies to date have examined the effects of SNP on psychosis symptom improvement with mixed results. In one study, a single infusion of SNP resulted in an immediate improvement in overall psychosis and negative symptoms in an antipsychotic medicated ECS group with <5 years illness duration, an effect that persisted for 4 weeks¹⁹. However, four studies performed in chronic SZ did not find any evidence of symptomatic improvements, with two of these studies providing repeated infusions of SNP^{20–23}. There were several limitations with these negative studies: older patient population, longer durations of illness (8-17 years), and the absence of a treatment biomarkers. These studies neglected to consider an alternative mechanism of action for SNP, which would include the protection against inflammatory mediated microvascular dysfunction. Another important factor to consider is that while ~70 randomized control trials to date have examined adjunctive antiinflammatory drugs on psychosis symptoms or cognition in SZ²⁴, six of these have performed post hoc analyses of participants with elevated levels of individual inflammatory markers (such as CRP), and their findings strongly suggest that ECS individuals with elevated peripheral inflammation have the greatest benefit with anti-inflammatory drugs²⁴. Thus, it is conceivable that treatment effects could be stronger in participants with elevated markers of inflammation or disruptions in related pathways. As a result, in order to SNP to be effective it should be administered to patients with ECS. Thus, further work is needed to determine whether the effect of SNP treatment is dependent on a patient's illness duration and whether a retinal biomarker for microvascular dysfunction/inflammation can predict treatment response to SNP. There is a growing literature on how increased peripheral inflammation and

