-Risk C: Monitor therapy

Alfuzosin

Amphetamines

Clozapine and Chlorpromazine

Barbiturates

Benperidol

Blood Pressure Lowering Agents

Brigatinib

Brimonidine (Topical)

Dapsone (Topical)

Dexmethylphenidate

Diazoxide

DULoxetine

Herbs (Hypertensive Properties)

Herbs (Hypotensive Properties)

Local Anesthetics

Lormetazepam

Methylphenidate

Molsidomine

Naftopidil

Nicergoline

Nicorandil

Nitric Oxide

Pentoxifylline

Pholcodine

Prilocaine

Prostacyclin Analogues

Quinagolide

Sodium Nitrite

Sildenafil or Tadalafil

Yohimbine

References

- 1. Brown, H. E. *et al.* Efficacy and Tolerability of Adjunctive Intravenous Sodium Nitroprusside Treatment for Outpatients With Schizophrenia: A Randomized Clinical Trial. *JAMA Psychiatry* **76**, 691 (2019).
- Hallak, J. E. C. et al. Rapid Improvement of Acute Schizophrenia Symptoms After Intravenous Sodium Nitroprusside: A Randomized, Double-blind, Placebo Controlled Trial. JAMA Psychiatry 70, 668 (2013).
- 3. Stone J.M. et al. The effect of sodium nitroprusside on psychotic symptoms and spatial working memory in patients with schizophrenia: a randomized, double-blind, placebo-controlled trial. *Psychological Medicine* 46, 3443-3450 (2016).
- 4. Wang X. et al. Sodium nitroprusside treatment for psychotic symptoms and cognitive T deficits of schizophrenia: A randomized, double-blind, placebo-controlled trial. *Psychiatry Research* 269, 271-277 (2018).
- 5. Adelino et al. Treatment-resistant schizophrenia A RCT on the effectiveness of repeated-dose sodium nitroprusside. Schizophr Res. 2021 May;231:70-72.

B4. POSSIBLE BENEFITS

There are no direct benefits to subjects. However, as shown by previous clinical studies, an immediate improvement in overall psychosis and negative symptoms in participants with ESZ may be achieved with SNP treatment.

Potential benefits to society include increased understanding of the pathophysiology of schizophrenia and the personalization of treatment early in the course of schizophrenia illness. We are expecting to have an impact on the growing consensus in immunopsychiatry and neuro-ophthalmology that the retina provides a window into the brain that informs our understanding of brain pathophysiology and identifies biomarkers of treatment response with this study.

B5. POSSIBLE RISKS AND ANALYSIS OF RISK/BENEFIT RATIO

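### The marker analysis is a plain correlation with no arm term or between-arm comparison, so it cannot separate prediction of SNP benefit from prognosis

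*Combined protocol and SAP*

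**What the plan says.** The documents describe the marker question at two strengths.

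- **Prediction of response to SNP.** The protocol title reads "Proof of Mechanism Study using a Retinal Biomarker to Predict Treatment Response with Intravenous Sodium Nitroprusside". The hypothesis in B1 is that "this change can be predicted by retinal vessel morphology or CRP levels". The background in B2 says further work is needed on "whether a retinal biomarker for microvascular dysfunction/inflammation can predict treatment response to SNP". B4 (Possible Benefits) hopes for work that "identifies biomarkers of treatment response with this study".
- **Association only.** Purpose 2 in B1 asks "whether baseline retinal microvasculature or inflammation (CRP levels) correlate with a change in psychosis symptoms or cognition".

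The Outcome paragraph of B3.A sits nearer the first. It relates baseline or change in the markers to "the change in psychosis symptoms and cognition after SNP treatment compared to placebo".

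The method is one sentence in B3.B Statistical Considerations: "The relationship between baseline or change in retinal vessel measures or CRP and change in PANSS scores or cognition will be performed using" Pearson's or Spearman's correlation. It does not mention treatment arm, an interaction or a comparison of correlations between arms. It does not say whether the arms are pooled, analysed separately, or restricted to SNP. The mixed ANOVAs in the same section have a group factor but no marker term, and no analysis population is defined elsewhere.

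**The concern.** A marker predicts benefit from SNP only if the SNP-placebo difference varies with the marker. That is a statement about two arms, and a single correlation does not test it.

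**Baseline markers.** A purely prognostic marker tracks change equally well on placebo. It will still correlate with change in the pooled sample and in the SNP arm alone. If the correlation is run in each arm without a formal comparison, significance in SNP but not in placebo will often occur by chance.

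**Change in marker against change in PANSS.** If the arms are pooled and SNP shifts both variables, the two arm means alone produce a correlation, even when the variables are unrelated within each arm. Baseline markers escape this second problem, because randomisation makes them independent of arm.

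At stake is the claim in the title. A marker of natural course could be reported as predicting response to SNP, or two separate drug effects could be read as a mechanism.

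**Working it through.** **Inputs from B3.B (power calculation).** 16 per arm; two-sided alpha 0.05; PANSS difference 10 with SD 6, so d = 10/6 = 1.67 SD; retinal difference 0.007 with "estimated standard deviations of skeletal density =0.008", so q = 0.007/0.008 = 0.875 SD.

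**Assumptions.** The documents give no marker-outcome correlation, so r is shown as a range. The two SDs are treated as SDs of change, which the documents do not state.

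**The plan's own figures.** Normal approximation, power = Φ(effect × √(16/2) − 1.96):
- PANSS: 1.667 × 2.828 = 4.714, giving 99.7% (99.5% by the t-test), consistent with the stated figure of more than 80%.
- Retina: 0.875 × 2.828 = 2.475, giving 69.7% (66.8% by the t-test), against a stated figure of more than 70%.

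Neither figure concerns the marker-response question, for which no power is stated.

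**Purely prognostic baseline marker.** Simulation, 40,000 trials per scenario: change = r × marker + √(1−r²) × noise + d × arm, with the same r in both arms. Percentage of trials significant:

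| Analysis | r=0.1 | r=0.2 | r=0.3 | r=0.4 | r=0.5 |
|---|---|---|---|---|---|
| Pooled, d=0 | 9 | 19 | 39 | 64 | 85 |
| Pooled, d=0.5 | 8 | 19 | 37 | 61 | 83 |
| Pooled, d=1 | 8 | 16 | 32 | 53 | 75 |
| Pooled, d=1.67 | 7 | 13 | 24 | 40 | 59 |
| SNP arm only | 6–7 | 11 | 21 | 35 | 53 |
| SNP significant, placebo not | 6 | 10 | 16 | 23 | 25 |
| Arm × marker test, or Fisher z | 5 | 5 | 5 | 5 | 5 |

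Two rows can be checked by hand:
- A drug effect dilutes the pooled correlation to r/√(1+d²/4). At r=0.5 and d=1.67 this is 0.5/√1.694 = 0.38, hence the lower rates.
- The SNP-but-not-placebo rate is p(1−p), where p is the single-arm rate. At r=0.5 this is 0.53 × 0.47 = 0.25.

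Three comparisons show what each analysis can and cannot distinguish:
- The SNP-only correlation is significant in about 53% of trials whether r is 0.5 in both arms (prognostic) or 0.5 in SNP and 0 in placebo (predictive).
- With r of 0.5 in SNP and −0.5 in placebo, the pooled test is significant in about 7% of trials and the interaction in about 82%.
- With an unrelated baseline marker and d=1.67, the pooled test rejects in about 5%. A drug effect alone does not create a baseline-marker correlation.

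**Change on change, pooled, no within-arm association.** Induced r = (dq/4)/√[(1+d²/4)(1+q²/4)]. At d=1.667 and q=0.875 this is 0.365/√(1.694 × 1.191) = 0.365/1.421 = 0.26.

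| PANSS effect d | Retinal effect q | Significant |
|---|---|---|
| 1.67 | 0.875 | 31% |
| 1.67 | 0.5 | 14% |
| 1.67 | 0.25 | 7% |
| 1.0 | 0.875 | about 17% |
| 0.5 | 0.875 | 8% |
| 0.5 | 0.5 | 6% |

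An arm-adjusted or SNP-only correlation stays at 5%.

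**What the between-arm comparison can detect.** Fisher z, SE = √(2/13) = 0.392. For r of 0.5 versus 0: atanh(0.5)/0.392 = 0.549/0.392 = 1.40, and Φ(1.40 − 1.96) = 29%. The simulated interaction test gives 28%. For 0.3 versus 0, power is 12%. Power of 80% needs r of about 0.80 versus 0, since tanh(2.80 × 0.392) = 0.80.

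**The case against.** The strongest reply is that the contrast with placebo is already named in the Outcome paragraph, and that correlations are not the wrong tool, since comparing the two arm-specific coefficients by Fisher z would answer the question. This correctly locates the defect: what is missing is the comparison. But an outcome statement is not an analysis, and B3.B supplies no method that delivers it.

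Purpose 2 asks only for correlation, and B3.B matches that wording. That is true, and plain correlations would be adequate if nothing more were claimed. The title, the hypothesis and B2 do claim more. The B4 sentence is about societal benefit and carries little weight.

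The sizes rest on assumptions. This stands:
- At r of 0.1 the rates are barely above 5%.
- The largest pooled figures assume no drug effect, where a claim to predict SNP benefit would be least credible.
- The 0.875 SD retinal effect comes from figures attributed to pilot imaging data. It is not stated to be an effect on change from 0 to 5 hours, so 31% is an upper end.
- These rates are not false positives for the correlation itself. The association is real, and the error lies in calling it predictive.

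Finally, the proposed test has low power in a pilot of 32. That is a reason to report an interval and soften the claim. It does not make a test of a different question adequate.

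**Conclusion.** The concern holds. As written, the marker analysis cannot support a statement that a retinal measure or CRP predicts response to SNP. For an assumed prognostic correlation of 0.3 to 0.5, every reading of the sentence (pooled, SNP-only, or by arm without a formal comparison) would flag a merely prognostic marker in 16 to 85% of trials, depending on the reading and the drug effect, against about 5% for a formal comparison. The excess shrinks at weaker correlations and nearly vanishes at 0.1. The change-on-change problem arises only if arms are pooled and depends on the size of both drug effects. This is a secondary question in a pilot, but it is the question in the title, and it should be fixed.

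**What to change.** **Baseline markers.** Regress PANSS change, and separately cognition change, on baseline score, arm, baseline marker and arm × marker. Report the interaction with its 95% confidence interval as the test of prediction, labelled exploratory, and give the arm-specific slopes as description. A Fisher z comparison of the two arm-specific correlations is an acceptable alternative.

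**Change measures.** Use arm-adjusted (pooled within-arm) correlations and show each arm.

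**Both.** State the analysis set and the time point at which change is taken. If the plain correlations are kept instead, call them exploratory associations and make no claim that a marker predicts response to SNP.

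**Cost.** A few lines of wording and no new data. The price is a more modest claim. For r of 0.5 versus 0, power is about 27% with a baseline score unrelated to change, and about 36% if baseline score explains a further 25% of the variance. The 95% interval has a half-width of about 2.05 × √[(0.75+1.00)/15] = 0.7 SD of PANSS change per SD of marker. About 60 per arm would be needed for 80% power.
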